4. ANTICIPATED RISKS

During the COVID-19 pandemic, the health and safety of participants, researchers, and DRP staff is a primary focus. The study team will work with participants to determine preference for in-person or remote participation

in assessment and intervention sessions. Participants will have the option of either in-person or remote engagement throughout the study. The study team will also ensure that remote interviews are conducted within the participant's existing daily routine, ensuring participants are not exposed to settings or situations that will put them at any additional risk for viral exposure. If participants elect to meet remotely with the peer, they will complete remote study sessions by phone or video conferencing at their home, or other preferred private location.

The risk from research interviews is minimal and relatively uncommon. During assessments, participants may be uncomfortable discussing their drug use, depression, and other mental health symptoms. Participants may become frustrated and tense when they encounter difficulty when completing these measures.. The research team will be trained by [name] to be vigilante and sensitive to these signs of participant distress using role plays, didactics, and ongoing supervision and training in order to minimize any potential discomfort at ensure staff competence to detect and address participant distress. Participants will take breaks when necessary to help alleviate any discomfort. Participants will be reminded that they can refuse to answer any questions that make them uncomfortable and may take breaks whenever they are needed.

Behavioral Activation (BA) is a minimal risk intervention; however, the study population, adults with problematic substance use/SUD, is a group with potential to report symptoms of depression or anxiety. BA sessions may cause some temporary anxiety or distress due to discussing drug use and attempts to maintain abstinence. Through Michigan Peer Recovery Specialist Certification, the PRC interventionist will have received training to recognize signs of distress. We will take specific precautionary steps to protect against related risks to participant wellbeing. Researchers will contact one of the licensed psychologists on the team (Drs. [name], [name], or [name]) if a participant is in distress or reports current suicidality during interviews at any of the study assessment time-points or BA sessions (in-person or remote). If a research staff member, suspects that a participant is at active and imminent risk for suicide (determined using the Suicide Risk Assessment form), we will follow the preferred safety procedures at the treatment center including contacting DRP staff while the participant waits with the researcher (in person) or the participant remains on the phone with the researcher (remote). In the unlikely event that the research team is concerned about the participant's immediate safety while the participant is not at DRP, emergency services will be contacted and DRP staff will be notified. The researcher will work to stay in direct communication with the participant until emergency services have arrived at their location. The study PI will be immediately notified of any such occurrence once the participant is safe.

Special vulnerable populations, such as fetuses, neonates, children, prisoners, and institutionalized individuals will not be enrolled in this study. All interventionists will be watchful regarding the participant's status, and any concerns will be discussed with the Principal Investigators (PIs) and treatment team as needed. It will be made clear to participants during informed consent that they are free to terminate participation in the project at any time without any penalty.

There is a risk of breach of confidentiality if the online REDCap system at Henry Ford Health Systems, or Box through the University of Maryland, College Park. We will take the necessary precautions to minimize these risks to the best of our ability. All data will be coded with an ID number that is unique. All data including information from chart reviews, therapist reports and laboratory results will be labeled by ID only. Only the study team will have access to the link between the ID and participant's name. Data containing names and personal information will never be included in published materials. Electronic data files with identifiable information will be maintained separately from other data files and will only be used for administrative purposes (e.g., preparing aggregate reports to share with the study team). Participant identifiers and related PHI will be stored on secure servers, in a password protected file, accessible only by study staff and via a password protected computer. All

personnel will receive certification in human subjects' protection prior to beginning work on this project.

There is a possible risk to confidentiality if telecommunication services (telephone, or Zoom) are breached. In order to minimize this risk, the phone number provided to participants will be a secure, study-only issued phone. Only study personnel will have access to the phone. Participants' voice mails will be deleted once their contact details are updated on a secure, HIPAA compliant HFHS drive (Box). When using Zoom, security features will be in place to ensure that only the intended participant are allowed to join the call. All recordings of Zoom calls will be recorded to a local drive, uploaded into a secure UMCP Box folder, and deleted from the local drive upon upload. Prior to recording sessions, researchers and participants will discuss telecommunication guidelines to agree on appropriate behaviors and privacy expectations (e.g. remaining in one place during the session, ensuring both researcher and participant are in private spaces, etc.).

During trial assessments or BA sessions, it is possible that information may be disclosed about childhood abuse and neglect experiences and/or alleged perpetrators of abuse. We are aware of our obligation to report, and will follow the State of Michigan's mandatory child maltreatment reporting laws to the extent that reporting does not violate any applicable federal rules or policies. For this study, we state explicitly our responsibility to report in the body of the consent form.

There is a slight risk of potential for coercion (compensation). Compensation is linked to completion of research assessments as well as attendance of intervention sessions. Participants will be paid \$10 for the baseline assessment and intervention sessions 1-2, \$15 for intervention sessions 3-4 and the midpoint assessment, \$20 intervention sessions 5-7, and \$25 for intervention session 8, the post-treatment assessment and exit interview. The maximum compensation for this study accumulates to \$260 with all sessions, assessments, and the exit interview completed. This compensation is modest and reasonable for the tasks being requested and are consistent with other clinical intervention research trials.

Other risks: One risk in this study related to SUD and its treatment is the stress of and symptoms associated with withdrawal; these will be monitored and treated by the participant's treatment team at the DRP and any worsening of these identified by the study team or study interventionists will be reported to the DRP.

Throughout the study, the PIs and members of the research team will ensure strict adherence to study procedures according to the IRB-approved protocol. Should there be any protocol deviations or unanticipated problems, a PI will notify the HFHS IRB.

Because study sessions may be conducted virtually with participants and researchers at separate locations, the research team will be trained to exhibit hypervigilance when monitoring verbal, audible, and visual signs of participant distress. Researchers will discuss these signs in trainings and during weekly meeting discussions. The study interventionist will be a trained and supervised PRS who will receive training in procedures for responding to symptoms and in safety protocols designed as part of this study. Close supervision will be provided by the PI and co-Is who are licensed psychologists ([name] or [name]) as well as DRP clinical supervisor ([name]). The PRS will be watchful regarding the participant's status, and any concerns will be discussed with the Principal Investigator (PI) and treatment center as needed. It will be made clear to participants during informed consent that they are free to terminate participation in the project at any time without any penalty.

Adverse Events (AEs) are any untoward or unfavorable occurrence in a study participant, including any abnormal signs, symptoms, or disease, temporally associated with the participants' involvement in the research, whether or not considered related to participation in the research. Serious Adverse Events (SAEs) include any adverse

event that results in death, is life threatening, or places the participant at immediate risk of death from the event as it occurred, requires or prolongs hospitalization, causes persistent or significant disability or incapacity, results in congenital anomalies or birth defects, or is another condition which investigators judge to represent significant hazards. Unanticipated Problems (UPs) are defined as any incident, experience, or outcome that is unexpected (in nature, severity, or frequency), related or possible related to participation in the research, and suggests that the research places participants or others at a greater risk of harm (including physical, psychological, economic, or social harm) than was previously known or recognized.

For reporting of AEs and SAEs, the interventionist or other member of the research team will immediately notify a principal investigator. The investigator ([name] or [name]) will determine how to classify the event. AEs or SAEs will be classified according to severity, expectedness, and potential relatedness to the study intervention. Severity classifications will be: mild, moderate, or severe. Classification will be informed by the severity of the event and the degree of inconvenience or interruption of the participant's daily activities. Expectedness classifications will be: unexpected or expected. Unexpected classification will occur when the nature or severity of the event is not consistent with the information about the individual, the population, or the intervention. Relatedness classifications will be: definitely related, probably related, possibly related, or not related. Classification will be informed by temporal sequence and known/expected response patterns.

After determining the severity of the event and whether study-related, this information will be communicated to the rest of the research team. The research team, under [name] supervision, will complete HFHS IRB's Problem Event Form and submit to the IRB. Unanticipated SAEs that are definitely or possible related to the study will be reported to the IRB within two business days once reported to the PI. The expedited Problem Event report will be followed by a detailed, written report as soon as possible. All other AEs will be collected on an AE form. AEs will be communicated to the PIs during weekly study meetings and a summary will be reported to the IRB with annual review. UPs that impact risks to study participants or others will be reported to the IRB within two business days. Deaths will be reported by study staff to the PIs ([name] and [name]) immediately, and undergo expedited reporting to the IRB, within one business day of being reported to the PI.

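### The two-business-day SAE reporting rule skips the protocol's own probably related class, leaving a narrow group of non-fatal serious events with no stated expedited deadline

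*Protocol*

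**What the plan says.** All the relevant rules are in the adverse event text of Section 4 (Anticipated Risks), with a partial repeat in Section 12 (Data and Safety Monitoring Plan).

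- **Scale.** "Relatedness classifications will be: definitely related, probably related, possibly related, or not related".
- **Expedited SAE rule.** "Unanticipated SAEs that are definitely or possible related to the study will be reported to the IRB within two business days". The clock is stated as "within two business days once reported to the PI".
- **Residual rule.** "All other AEs will be collected on an AE form". The next sentence says "AEs will be communicated to the PIs during weekly study meetings" and provides for a summary to the IRB at annual review.
- **First notification.** "For reporting of AEs and SAEs, the interventionist or other member of the research team will immediately notify a principal investigator".
- **Unanticipated Problems (UPs).** Those that affect risks to participants or others go to the IRB in two business days. To be a UP, an event must be unexpected, at least possibly related, and one that "suggests that the research places participants or others at a greater risk of harm" than was known before.
- **Deaths.** Reported to the IRB within one business day of reaching the PI, with no relatedness condition.
- **Section 12.** Unanticipated adverse events go to the IRB under that board's policy. The protocol states no time limit there and no relatedness condition.

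**The concern.** The investigator must place each event in one of four classes, and the reporting deadline depends on that class. The SAE rule names the top and bottom related classes and leaves out the one between them. Anyone applying the text as written would report a possibly related serious event faster than a probably related one, which reverses the order that the scale implies. Section 4 also commits the PIs to strict adherence to the IRB-approved procedures, so the literal wording matters. What is at stake is prompt IRB sight of a serious event that the investigator thinks is probably due to the study. The protocol itself anticipates that suicidality and withdrawal symptoms may arise in this population, and a hospitalisation or a life-threatening event would meet its SAE definition.

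**Working it through.** No figure in the plan needs to be reproduced, and no arithmetic applies. The check is to take an unanticipated SAE, assign it to each relatedness class in turn, and follow every reporting route that the protocol gives. I read unanticipated in the SAE rule as the unexpected class of the protocol's expectedness grading.

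**Step 1: is an SAE not named in the expedited rule caught by the residual rule?** Yes. Section 4 defines SAEs as adverse events meeting a seriousness criterion, so they are a subset of AEs, and "All other AEs will be collected on an AE form" takes in any SAE that the preceding rule does not cover.

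**Step 2: routing of a non-fatal, unanticipated SAE, read literally.**

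| Class | Named in SAE rule? | Stated deadline to the IRB |
|---|---|---|
| Definitely related | Yes | 2 business days |
| Probably related | No | 2 business days only if also judged a UP; otherwise AE form and annual summary |
| Possibly related | Yes | 2 business days |
| Not related | No | AE form and annual summary |

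One of the three related classes is left out.

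**Step 3: do the other routes restore the deadline?**

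- *Deaths.* Yes, within one business day. The gap is therefore confined to non-fatal events.
- *UP rule.* In part. A probably related event meets the relatedness condition, but it must also suggest greater risk than previously known. The SAE rule has no such condition. A possibly related SAE is thus expedited without that judgement, and a probably related one is expedited only with it.
- *Section 12, unanticipated adverse events.* This gives a route to the IRB outside the annual summary, but no time limit is stated in the protocol. The IRB policy it relies on is not part of the documents.
- *Problem Event Form.* Section 4 has the team complete and submit this form after classification. The sentence is not limited by class and gives no general deadline.

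What remains is an event that is serious, non-fatal, unanticipated, probably related and not judged a UP.

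**Step 4: the two sentences on notifying the PI.** The opening sentence covers AEs and SAEs alike and requires that "the interventionist or other member of the research team will immediately notify a principal investigator". The later sentence, "AEs will be communicated to the PIs during weekly study meetings", mentions AEs only and comes straight after the residual rule. For SAEs the only stated route to the PI is the immediate one. For ordinary AEs both timings appear, and the text does not say that the weekly one is additional.

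**The case against.** The strongest reply is that this is a drafting slip with little practical effect. On an ordered scale, a rule that names the classes on either side of *probably* is most naturally read as including it, and the UP definition uses possible relatedness as a floor in much the same way. Section 4 describes the intervention as minimal risk, so an unexpected, serious, probably related event would ordinarily suggest greater risk than previously known and would be reported as a UP within two business days. The text between the Section 12 repeat of the definitions and classification and the references was also unavailable, and it may restate the time limits.

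Most of this stands as a description of how small the gap is. It does not remove the gap: a safety deadline should not depend on staff inferring a missing class, and UP status is a separate judgement that the SAE rule does not require. Nothing can be inferred either way from the unavailable text.

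A reader might go further in two directions that the documents do not support. The first is that the immediate and weekly sentences together let a serious event wait up to a week before the SAE clock starts. The opening sentence names SAEs and requires immediate notification, and the weekly sentence follows the residual rule and mentions only AEs, so it does not delay that clock. The second is that every probably related SAE waits for the annual summary. That overlooks the death rule, the UP rule and the Section 12 route.

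**Conclusion.** The expedited SAE rule does not match the protocol's own relatedness scale and, followed literally, gives an inverted result for one of the three related classes. The affected events are non-fatal, unanticipated, probably related SAEs not judged to be UPs. For these the stated deadline changes from two business days to none, with the annual summary as the only dated IRB report in Section 4. The documents give no SAE rates, so the expected number of such events among at most 40 participants cannot be estimated; it is likely to be small. The immediate and weekly wording is a separate, minor inconsistency about ordinary AEs and is not a cause of the gap.

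The conclusion rests on a literal reading, on SAEs being a subset of AEs as the protocol defines them, and on the text available for review. It has no bearing on the sample size or on the outcomes in the SAP.

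**What to change.** Reconcile the expedited SAE sentence in Section 4 with the relatedness scale in the paragraph before it, so that each related class has a stated reporting route and none is skipped. If the time limits are restated in Section 12, make the same correction there. As a minor edit, reconcile the two sentences on notifying the PI so that weekly discussion of AEs is clearly additional to first notification. The cost is one sentence for the main point and one for the minor point in a protocol amendment, with negligible workload and no change to data collection or analysis.

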5. ANTICIPATED BENEFITS

There are no direct, guaranteed benefits to the participants. However, it is possible that receipt of BA will result in improved treatment outcomes and reduce drug use for participants.

From a broader perspective, this study may significantly add to the field by increasing our understanding of ways to integrate evidence-based behavioral interventions to support treatment adherence through PRC delivery. Supporting SUDoutcomes could help to promote greater recovery in communities hit hard by substance use, particularly in low-income, underserved areas, such as our study site in Detroit.

6. RENUMERATION/COMPENSATION

Open-label trial participants will receive \$10 for the baseline assessment and intervention sessions 1-2, \$15 for intervention sessions 3-4 and the midpoint assessment, \$20 intervention sessions 5-7, and \$25 for intervention session 8, the post-treatment assessment and exit interview. The maximum compensation for this study accumulates to \$260 with all sessions, assessments, and the exit interview completed. This compensation is modest and reasonable for the tasks being requested and are consistent with other clinical intervention research trials.

7. COSTS

Participation in this study may involve transportation and parking costs. These costs will not be the responsibility of the investigator, however, we will compensate participants per session in order to indirectly offset costs.

8. ALTERNATIVES

The alternative is that subjects do not have to participate in the research and continue in treatment as usual.

9. CONSENT PROCESS AND DOCUMENTATION

A trained research staff member will conduct the informed consent. The researcher will read the consent form aloud to the participant and ensure that the participant understands key points from the consent form and what is being asked of them in participation. Participants may also choose to read the consent form themselves. Prior to giving their informed consent, participants will be given the chance to ask questions, and the researcher or trained designee will answer all the questions, making sure that the participants are satisfied and comprehend study procedures (see Evaluation to Sign Consent Form). Participants will also be informed about the voluntary nature of the study, and their right to withdraw at any point. If the participant refuses to consent, they will be considered a refusal and therefore ineligible for the study.

Before written consent is given, the participant: 1) should verbalize understanding; 2) should be given the opportunity to ask questions; 3) should be given time to read the consent; 4) should report all questions were answered to their satisfaction; and 5) must correctly answer the questions on the evaluation to sign consent document. When completing the evaluation to sign consent form, the researcher or trained designee will ask questions 1 through 3 to ensure that the participant understands the risks, understands what will be expected of them, and understands that they may drop out at any point during the study.

After written consent is given, the participant will be given a copy of consent form with signature blocks removed. Consent forms will be locked in a secure location at the Detroit Recovery Project.

The consent process will take place after a participant is deemed potentially eligible based on initial screening questions and expressed interest in participation and before a potentially eligible participant proceeds with the baseline assessment. Participants will be reminded that they can stop participating in the study at any time, and that all aspects of this study are voluntary.

10. WITHDRAWAL OF SUBJECTS

Subjects may voluntarily withdraw from the study at any time with no penalty themselves or their healthcare or insurance plans/benefits. In the event of safety concerns and/or due to the participant having exceptional difficulties with completing the questionnaires, the PI may decide to withdraw the participant from the study.

11. PRIVACY AND CONFIDENTIALITY

For this study, we will ensure the separation of de-identified participant data from protected health information (PHI) by storing data in separate locations. De-identified data will be stored using secure, password-protected software hosted on UMCP and HFHS servers (e.g. REDCap and Box) and in double-locked rooms at the DRP. At DRP, all participant information will be referenced using participant identification numbers. De-identified participant responses to study measures will be collected and stored using REDCap, a software toolset and workflow methodology for electronic collection and management of data. De-identified audio recordings and transcripts will be stored on secure, password-protected UMCP Box folders. Only the investigators/authorized

staff will have access to the REDCap database and the Box folder.

We will immediately destroy initial screening checklists for individuals who are deemed ineligible after DRP program initiation. We will only keep a record of number of screenings completed and reasons for ineligibility.

We will need to collect names and demographic information for participants who complete consent. Once collected, data will be de-identified. The file containing the information that links participant names to their IDs will again be stored in password-protected files on the HIPAA compliant, secure RedCap file. Only investigators will have access to this file. The key linking identifiable information to the participant ID will be destroyed five years after publication of study results.

Audio-recordings will be uploaded to UMCP's Box folder immediately following the session, and the audio file will be deleted from the digital recorder. These computer audio files will be secured by Box dual authentication and only accessible by authorized study personnel. The purpose of the audio-recordings will be explained to all participants and we will obtain both informed consent and authorization for recording. Participant confidentiality will be respected.

All physical data, including filled out questionnaires, will be stored at the DRP in locked drawers. Once data are collected, all data will be de-identified, i.e. names will be removed and participants will be assigned ID numbers.

As part of the informed consent process, participants will be advised that they may decline to answer any questions. This will provide participants with the assurance of confidentiality around sensitive personal information relating to substance use and mental health. All personnel working on the project will be educated about the importance of respecting participants' rights to confidentiality. Investigators will all complete and maintain ethical and CITI training. All study personnel will be appropriately trained in the ethical conduct of human subjects' research.

Audio-recordings for participant exit interviews be transcribed by trained members of the research team (IRB-approved staff member or student with up-to-date CITI training). Any inadvertent disclosure of personally identifiable information will be redacted upon transcription.

Study files will be maintained until five years after the publication of study results in line with the guidelines of the American Psychological Association.

Due to Michigan law, we will disclose to the appropriate individuals and/or authorities any information that comes to our attention concerning child abuse or neglect, or thoughts of harm to self or others, or if a court of law ensures, a subpoena for the research records.

Important HIPAA Concerns

If you will be using, disclosing or accessing the health record (medical record, mental health or substance abuse records, etc) for research purposes, then HIPAA applies. If you are accessing medical records or PHI for screening purposes, HIPAA regulations apply and investigators will need to obtain prospective HIPAA authorization or apply for a waiver of HIPAA authorization for the screening activities, as applicable, depending on the nature of the study.

If accessing PHI for screening purposes and providing written authorization, describe how authorization will be obtained for the screening portion, who will obtain it or request and justification for a request for HIPAA waiver for recruitment purposes. If you are requesting waiver of HIPAA for screening purposes,

describe the confidentiality procedures that will be used.

For more information on HIPAA authorization guidance, visit: <https://www.hhs.gov/hipaa/for-professionals/privacy/guidance/research/index.html>

NOTE: You may also need to obtain a waiver of documentation of informed consent (ie, signed consent) for screening purposes if you do not meet the requirements for waiving consent provided in the Consent Process section.

